6.2. Treatment Phase: Treatment Assessments

6.2.1. Day 1 Assessments

After confirmation of eligibility has been evaluated, the following tests and procedures must be completed on Day 1 prior to enrollment and dosing/dispensing:

- Confirm eligibility
- Perform complete physical examination
- Vital signs
- Body weight
- Assessment of AEs and concomitant medications
- Pregnancy prevention counseling
- Assess presence and severity of ascites and hepatic encephalopathy for CPT score
- Perform 12-lead ECG
- Subject completes Health Related Quality of Life Questionnaire: SF-36, CLDQ-HCV, FACIT-F, and WPAI
- Obtain blood samples for:
 - Hematology
 - Chemistry
 - Coagulation tests

— HCV RNA

— Viral sequencing

PPD

PPD

— HBV DNA (only in subjects who are HBcAb+ at Screening)

- Obtain urine samples for the following procedures:

— Urinalysis

— Urine pregnancy test for females of childbearing potential only

6.2.2. Study Drug Administration

- Dispense study drugs as directed by the IWRS
- Instruct the subject on the packaging, storage and administration of study drug
- Observe the subject taking the first dose of study drugs and record the time of first dose and whether it was taken with or without food

6.2.3. Week 2 (± 3 days)

The following procedures/assessments are to be completed at this visit:

- Vital signs
- Body Weight
- Assessment of AEs and concomitant medications
- Assess presence and severity of ascites and hepatic encephalopathy for CPT score
- Obtain blood samples for:
 - Hematology
 - Chemistry
 - Coagulation

- HCV RNA
- Viral sequencing
- Single PK
- Assess adherence with the study drug dosing regimen including pill count

6.2.4. Weeks 4 and 8 (\pm 3 days)

- Assess presence and severity of ascites and hepatic encephalopathy for CPT score
- Vital signs
- Body Weight
- Assessment of AEs and concomitant medications
- Pregnancy prevention counseling
- Obtain blood samples for:
 - Hematology
 - Chemistry
 - Coagulation
 - HCV RNA
 - Viral sequencing
 - Single PK
 - HBV DNA (only in subjects who are HBcAb+ at Screening)
- Obtain urine sample for:
 - Urine pregnancy test for females of childbearing potential only
- Review study drug compliance with subject (subject should return all study drug at these visits)
- Dispense study drug as directed by the IWRS

6.2.5. Week 12 (\pm 3 days) or Early Termination

- Perform complete physical examination
- Assess presence and severity of ascites and hepatic encephalopathy for CPT score
- Vital signs
- Body weight
- Assessment of AEs and concomitant medications
- Pregnancy prevention counseling
- Subject completes Health Related Quality of Life Questionnaire: SF-36, CLDQ-HCV, FACIT-F, and WPAI
- Obtain blood samples for:
 - Hematology
 - Chemistry
 - Coagulation tests
 - HCV RNA
 - Viral sequencing
 - PPD 
 - Single PK
 - HBV DNA (only in subjects who are HBcAb+ at Screening)
- Obtain urine samples for the following procedures:
 - Urinalysis
 - Urine pregnancy test for females of childbearing potential only
- Review study drug compliance
- Subjects should return all bottles of study drug at the Week 12 Visit

6.3. Posttreatment Assessments

6.3.1. 4-Week Posttreatment Visit (\pm 5 days)

- Assess presence and severity of ascites and hepatic encephalopathy for CPT score
- Vital signs
- Body Weight
- Assessment of AEs and concomitant medications
- Pregnancy prevention counseling
- Obtain blood samples for:
 - Hematology
 - Chemistry
 - Coagulation
 - HCV RNA
 - Viral sequencing
 - HBV DNA (only in subjects who are HBcAb+ at Screening)
- Obtain urine sample for:
 - Urine pregnancy test for females of childbearing potential only

6.3.2. 12 & 24 Week Posttreatment Visit (\pm 5 days)

- Assess presence and severity of ascites and hepatic encephalopathy for CPT score
- Vital signs
- Body Weight
- Perform symptom-directed physical examination
- Pregnancy prevention counseling
- Subject completes Health Related Quality of Life Questionnaire: SF-36, CLDQ-HCV, FACIT-F, and WPAI at posttreatment Week 12 only

- Obtain blood samples for:
 - Hematology
 - Chemistry
 - Coagulation
 - HCV RNA
 - Viral sequencing
 - HBV DNA (only in subjects who are HBcAb+ at Screening)
- Obtain urine sample for:
 - Urine pregnancy test for females of childbearing potential only

6.4. Assessments for Premature Discontinuation from Study

If a subject discontinues study drug (for example, as a result of an AE), every attempt should be made to keep the subject in the study and continue to perform the required study-related follow-up and procedures (see Section 3.4.1, Criteria for Discontinuation of Study Treatment). If this is not possible or acceptable to the subject or Investigator, the subject may be withdrawn from the study.

6.5. Procedures and Specifications

6.5.1. Clinical Laboratory Analytes

Hematology: Hematocrit, hemoglobin (Hb), platelet count, red blood cell count (RBC), white blood cell count (WBC) with differential (absolute and percentage) including lymphocytes, monocytes, neutrophils, eosinophils, basophils, reticulocyte count and mean corpuscular volume (MCV).

Coagulation: International normalized ratio (INR), prothrombin time (PT), activated partial thromboplastin time (APTT)

Chemistry: Alanine aminotransferase (ALT/SGPT), aspartate aminotransferase (AST/SGOT), albumin, alkaline phosphatase, creatinine, total bilirubin and direct bilirubin, glucose, lipase, potassium, sodium, phosphate, uric acid, and creatine kinase (CK),

Urinalysis: blood, glucose, leukocyte esterase, pH, protein, urobilinogen. Reflex to microscopic urinalysis if dipstick result is abnormal.

Virological Tests: Serologies for HCV and HBV. HBV DNA (only in subjects who are HBcAb+ at Screening). Serology and/or antigen testing for HIV (including reflex testing) as

necessary, HCV RNA will be measured using the COBAS[®] AmpliPrep/COBAS[®] TaqMan[®] HCV Test, v2.0 for Use with the High Pure System. HCV genotype and subtype will be determined using the Siemens VERSANT[®] HCV Genotype INNO-LiPA 2.0 Assay. Gilead reserves the right to use alternate assays for HCV RNA and HCV genotype should the above assays become unavailable or the results are inconclusive.

IL28B genotype will be determined by polymerase chain reaction (PCR) amplification of the SNP, rs12979860, with sequence specific forward and reverse primers and allele specific fluorescently labeled TaqMan[®] MGB probes. Gilead reserves the rights to use alternate assays for IL28B determination should the above assay become unavailable.

Pregnancy Tests: Serum β -hCG, Urine β -hCG (if positive, requires immediate confirmation with Serum β -hCG)

Additional Tests: Urine drug screen (for amphetamines, cocaine, methadone, opiates), hemoglobin A1c (HbA1c), Fibrotest.

6.5.2. Medical History

Medical history including details regarding illnesses and allergies, date(s) of onset, and whether condition(s) is currently ongoing, and medication history will be collected on all subjects during screening. Obtain HCV treatment history as per Section 4.

6.5.3. Complete Physical Examination

A complete physical examination must include source documentation of general appearance, and the following body systems: Head, neck and thyroid; eyes, ears, nose, throat, mouth and tongue; chest (excluding breasts); respiratory; cardiovascular; lymph nodes, abdomen; skin, hair, nails; musculoskeletal; neurological.

6.5.4. Height & Weight Measurement

Height will be collected at Screening. Weight measurement will be collected at each study visit. The difference in body weight measurements between Day 1 and End of Treatment will be calculated.

6.5.5. Vital Signs

Assessment of vital signs will include measurement of resting blood pressure, pulse, respiratory rate, and temperature.

Blood pressure will be measured using the following standardized process:

- Subject should sit for ≥ 5 minutes with feet flat on the floor and measurement arm supported so that the midpoint of the manometer cuff is at heart level;
- Use a mercury sphygmomanometer or automatic blood pressure device with an appropriately sized cuff with the bladder centered over the brachial artery;
- Measure and record the blood pressure to the nearest 2 mmHg mark on the manometer or to the nearest whole number on an automatic device.

6.5.6. Body Mass Index (BMI)

BMI is calculated by the following equation.

$$\text{BMI} = \frac{\text{weight (pounds)} \times 703}{(\text{height in inches})^2} \quad \text{or} \quad \frac{\text{weight in kilograms}}{(\text{height in meters})^2}$$

6.5.7. MELD and CPT Score Calculations

MELD score and CPT score will be calculated from the central laboratory values attained at each visit. Assessment of ascites and hepatic encephalopathy will be determined by the site as in below table and will be entered into the CRF. Besides calculating the CPT score at Screening (using central laboratory values) to determine eligibility, sites will not need to calculate these scores for subsequent visits.

6.5.7.1. MELD Score

The MELD score is calculated using the following formula {[MELD/PELD 2009](#)}:

$$\text{MELD} = 3.8[\text{serum bilirubin (mg/dL)}] + 11.2[\text{INR}] + 9.57[\text{serum creatinine* (mg/dL)}] + 6.43$$

Round to the nearest whole number. Laboratory values less than 1.0 are set to 1.0 for the purposes of the MELD score calculation.

* If subject has had dialysis twice within a week prior to the serum creatinine measurement, or is within 24 hours of continuous venovenous hemodiafiltration, then default to 4 mg/dL for serum creatinine value in MELD calculation.

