8.1.3. Secondary Endpoint

The secondary efficacy endpoints include the proportion of subjects who attain sustained virologic response at 4 and 24 weeks after cessation of the study treatment regimen (SVR4 and SVR24); the proportion of subjects who have HCV RNA < LLOQ by visit while on study treatment; CPT and MELD score changes from Day 1; absolute and change from Day 1 in HCV RNA through Week 12; and the proportion of subjects with virologic failure.

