8.3. Demographic Data and Baseline Characteristics

Demographic and baseline measurements will be summarized using standard descriptive methods.

Demographic data will include sex, self-identified race/ethnicity.

Baseline characteristic data will include body mass index, HCV RNA level (\log_{10} IU/mL), genotype of HCV infection, IL28B genotype, CPT score, MELD score and additional endpoints as necessary.

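### The MELD formula in Protocol section 6.5.7.1 has no logarithms, so scores computed as printed are far too high and some changes have the wrong sign

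*Protocol*

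**What the plan says.** Protocol section 6.5.7.1 presents its equation as the working definition: "The MELD score is calculated using the following formula". The equation multiplies bilirubin (mg/dL) by 3.8, INR by 11.2 and serum creatinine (mg/dL) by 9.57, adds the three products and adds 6.43. It cites a MELD/PELD calculator document as the source. The section then asks for rounding to a whole number and sets a floor: "Laboratory values less than 1.0 are set to 1.0 for the purposes of the MELD score calculation". For subjects on recent dialysis it gives a substitute value: "then default to 4 mg/dL for serum creatinine value in MELD calculation".

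Section 6.5.7 says how the score is obtained: "MELD score and CPT score will be calculated from the central laboratory values attained at each visit". After Screening, sites are not asked to calculate either score.

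The score is used in two places. Section 8.1.3 lists "CPT and MELD score changes from Day 1" among the secondary efficacy endpoints, in line with a secondary objective in section 2. Section 8.3 names it among the baseline characteristics: "IL28B genotype, CPT score, MELD score and additional endpoints as necessary". No other section gives a different formula or corrects this one.

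**The concern.** The equation and the floor do not fit together. If each laboratory value is logged, a floor of 1.0 has a clear job: log(1) is zero, so a value at or below 1.0 adds nothing and no term goes negative. In a linear sum a value below 1.0 causes no difficulty, and the floor only raises the score. The section therefore shows from its own content that logarithms were intended and are missing.

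If the equation is programmed as printed, the MELD baseline summary will describe scores on a scale that starts at 31. The change from Day 1 will also be wrong. A linear and a logarithmic score weight the same laboratory movement differently, so the error is not a constant that drops out on subtraction. When one component improves and another worsens, the two forms can disagree on whether the subject got better.

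**Working it through.** The protocol states no MELD value, so there is no figure to reproduce. The check compares the printed form with the same coefficients on logged values.

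**Inputs**
- Coefficients, constant and the floor of 1.0: section 6.5.7.1.
- Bilirubin at entry up to 10 mg/dL: section 4.3, exclusion 13g.
- INR and creatinine values in the examples: assumptions, chosen for illustration.
- Base of the logarithm: natural log, an assumption. The floor shows that a log is meant but does not fix its base. Base-10 results are shown where the choice matters.

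**Formulas** (each value floored at 1.0; b = bilirubin, i = INR, c = creatinine)
- Printed: P = 3.8b + 11.2i + 9.57c + 6.43
- Logged: L = 3.8 ln(b) + 11.2 ln(i) + 9.57 ln(c) + 6.43

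**Minimum score.** With b = i = c = 1, P = 3.8 + 11.2 + 9.57 + 6.43 = 31.00 and L = 6.43. The value 6.43 is the same for any base.

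**Smallest excess.** For x ≥ 1, x − ln(x) ≥ 1. Hence P − L ≥ 3.8 + 11.2 + 9.57 = 24.57 for every subject at every visit. The bound also holds for base 10.

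**Scores before rounding**

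| b / i / c | Printed | Natural log | Base 10 |
|---|---|---|---|
| 4 / 1.8 / 1.0 | 15.20 + 20.16 + 9.57 + 6.43 = 51.36 | 5.27 + 6.58 + 0 + 6.43 = 18.28 | 6.43 + 11.85/2.3026 = 11.58 |
| 10 / 2.4 / 1.5 | 38.00 + 26.88 + 14.36 + 6.43 = 85.67 | 8.75 + 9.81 + 3.88 + 6.43 = 28.87 | 6.43 + 22.44/2.3026 = 16.17 |

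Against natural logs the printed score is about 2.8 to 3.0 times as high at these profiles, and 4.8 times as high at the floor (31.00/6.43).

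**Change, one component moving.** Bilirubin 10 to 5, the rest fixed: printed 3.8 × (5 − 10) = −19.0; logged 3.8 × ln(0.5) = −2.63 (base 10: −1.14).

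**Change, components moving in opposite directions.** INR is fixed in both cases and drops out.
- Bilirubin 7 to 4, creatinine 1.0 to 2.0. Printed: −11.40 + 9.57 = −1.83. Logged: −2.13 + 6.63 = +4.51.
- Bilirubin 8 to 5, creatinine 1.0 to 1.3. Printed: −11.40 + 2.87 = −8.53. Logged: −1.79 + 2.51 = +0.72.

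A change of base divides both logged terms by the same constant, so the sign reversal does not depend on the base.

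**How often.** An illustrative simulation drew bilirubin from 1–10, INR from 1–2.5 and creatinine from 0.6–2.0 uniformly, with independent visit-to-visit variation of 0.2 (SD on the log scale). The rounded changes had opposite signs in about 7.5% of pairs. That figure depends entirely on these assumed ranges.

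**The case against.** Four points can be made on the other side.

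1. **The logs may have been lost in conversion.** An equation can lose a function name when a PDF is turned into text, and the brackets round each laboratory value would suit a function argument. This cannot be ruled out without looking at the printed page. It is unlikely, because the same token would have had to vanish from three terms that otherwise keep their coefficients, brackets, units and footnote asterisk.
2. **The exact replacement is not in the protocol.** This stands in part. The floor proves that a log is meant but not its base, and the cited calculator document was not available. The printed minimum of 31, the logged minimum of 6.43, the lower bound on the excess and the sign reversals do not depend on whether the base is e or 10. The other logged figures do.
3. **The harm depends on literal programming.** This also stands. The derivation is not done by sites after Screening, a programmer may follow the cited calculator, and section 8.4.2 leaves efficacy details to an analysis plan that was not available. A minimum of 31 would probably be noticed at first output. Still, the protocol prints this equation as the definition, and an analysis that silently departs from it creates a discrepancy of its own.
4. **The reach is limited.** Eligibility uses the CPT score (section 4.2). The stopping criteria, the primary endpoints and the sample size do not use MELD. Bilirubin, INR and creatinine are collected at every visit, so scores can be recomputed at any time. This limits the damage but does not remove the error.

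A worsening creatinine alongside a falling MELD is not in itself a sign of the error, since the logged score can also fall when a bilirubin gain outweighs a small creatinine rise. The fault lies in the cases where the two forms disagree in sign.

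**Conclusion.** The concern holds. The equation in section 6.5.7.1 is wrong as written, and the floor in the same section shows it. Applied literally, it gives no score below 31, overstates every score by at least 24.57 points, exaggerates a bilirubin-driven change (−19.0 against −2.6 in the example) and can reverse the direction of change.

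The consequences are confined to the MELD baseline summary and the MELD-change secondary endpoint, but there they affect every score. The conclusion assumes that the page itself shows no logarithm and that the derivation follows the page. The natural-log figures also assume base e, and the INR and creatinine values are illustrative.

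**What to change.** Correct the equation in section 6.5.7.1 to: MELD = 3.8 × ln(bilirubin, mg/dL) + 11.2 × ln(INR) + 9.57 × ln(creatinine, mg/dL) + 6.43. Keep the floor of 1.0, the rounding rule and the dialysis substitution as they are. Before issuing the change, confirm the natural-log base against the calculator document that the section cites, and look at the printed page to rule out a conversion loss.

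Then check that the central derivation and the SAS analysis programs use the logged form. A simple test is that all values at the floor must return 6 after rounding, not 31.

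The cost is a one-line protocol correction and a programming check. No extra data are needed, and no subject's treatment or eligibility changes.

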9.1.6. Case Report Forms

For each subject consented, an eCRF will be completed by an authorized study staff member whose training for this function is documented according to study procedures. eCRF should be completed on the day of the subject visit to enable the sponsor to perform central monitoring of safety data. The Eligibility Criteria eCRF should be completed only after all data related to

eligibility have been received. Subsequent to data entry, a study monitor will perform source data verification within the EDC system. Original entries as well as any changes to data fields will be stored in the audit trail of the system. Prior to database lock (or any interim time points as described in the clinical data management plan), the investigator will use his/her log in credentials to confirm that the forms have been reviewed, and that the entries accurately reflect the information in the source documents. The eCRF capture the data required per the protocol schedule of events and procedures. System-generated or manual queries will be issued to the investigative site staff as data discrepancies are identified by the monitor or internal Gilead staff, who routinely review the data for completeness, correctness, and consistency. The site coordinator is responsible for responding to the queries in a timely manner, within the system, either by confirming the data as correct or updating the original entry, and providing the reason for the update (eg, data entry error). At the conclusion of the trial, Gilead will provide the site with a read-only archive copy of the data entered by that site. This archive must be stored in accordance with the records retention requirements outlined in Section 9.1.5.

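### MELD fixes creatinine at 4 mg/dL under dialysis without capping it for other subjects, and no scheduled item collects the dialysis status that the rule needs

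*Protocol*

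**What the plan says.** Section 6.5.7.1 of the protocol fixes the MELD calculation. The score is a weighted sum of bilirubin, INR and creatinine plus a constant; creatinine carries a weight of 9.57 and, as printed, enters without a logarithm. There is a lower bound: "Laboratory values less than 1.0 are set to 1.0 for the purposes of the MELD score calculation". There is also a dialysis rule. It is triggered by "If subject has had dialysis twice within a week prior to the serum creatinine measurement", or by continuous venovenous hemodiafiltration within 24 hours, and it ends "then default to 4 mg/dL for serum creatinine value in MELD calculation". No upper limit is given for creatinine in other subjects.

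On data sources, Section 6.5.7 says: "MELD score and CPT score will be calculated from the central laboratory values attained at each visit". Sites enter ascites and encephalopathy in the CRF. After Screening, "sites will not need to calculate these scores for subsequent visits". Dialysis appears in none of the visit lists in Sections 6.1 to 6.3 and in no row of Appendix 2. Section 9.1.6 ties data capture to that schedule: "The eCRF capture the data required per the protocol schedule of events and procedures".

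Section 8.1.3 lists "CPT and MELD score changes from Day 1" among the secondary efficacy endpoints.

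**The concern.** There are two separate gaps.

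The first is in the scale. Dialysed subjects are held at 4 mg/dL while undialysed subjects keep whatever value is measured. Above 4 mg/dL the order reverses: the subject not yet on dialysis scores worse than the one on it, and starting dialysis lowers the score relative to the visit before. Such values are within what the protocol foresees, since Appendix 3 grades creatinine above 3.00 to 6.00 mg/dL as Grade 3 and above 6.00 as Grade 4.

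The second is in the data. A central laboratory creatinine does not show whether the subject was dialysed twice in the preceding week. For CPT, the protocol routes the two non-laboratory components through the CRF. For MELD, it provides no such route for the one non-laboratory condition. If dialysis goes unnoticed, a creatinine already lowered by dialysis enters the score.

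At stake is a secondary endpoint meant to show change in liver disease, in a single-arm study of about 50 subjects where individual MELD changes are likely to be read directly.

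**Working it through.** The protocol states no MELD result to reproduce, so the check evaluates the Section 6.5.7.1 formula with bilirubin and INR held fixed.

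**Inputs.** Creatinine weight 9.57; dialysis value 4 mg/dL; floor 1.0; entry limit CLcr 30 mL/min (Section 4.3); Cockcroft-Gault with actual body weight (Section 6.5.8). Two readings are carried throughout: the formula as printed (linear) and, as an assumption, natural logarithms of the laboratory values. Differences are before rounding to whole points.

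**Step 1. Visit-to-visit change when recorded dialysis starts.** With previous creatinine c, the change is 9.57 × (4 − c) as printed, or 9.57 × ln(4/c) on the log form.

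| Previous creatinine (mg/dL) | As printed | Log form |
|---|---|---|
| 2 | +19.14 | +6.63 |
| 3 | +9.57 | +2.75 |
| 4 | 0 | 0 |
| 5 | −9.57 | −2.14 |
| 6 | −19.14 | −3.88 |

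The score falls only from values above 4 and rises from values below. The same differences separate an undialysed subject from a dialysed one at a single visit. For example, with bilirubin 4 and INR 1.8 (illustrative), creatinine 6 gives a score of 99 and dialysis gives 80 as printed; on the log form, 35 and 32.

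**Step 2. Dialysis not captured.** If a post-dialysis value of 2.0 (assumed) is used instead of 4, the score is too low by 9.57 × (4 − 2) = 19.14 as printed, or 9.57 × ln(4/2) = 6.63 on the log form.

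**Step 3. What this does to change from Day 1.** Take a Day 1 creatinine of 1.0 (illustrative).
- Default applied: 9.57 × (4 − 1) = +28.71 as printed; 9.57 × ln 4 = +13.27 log.
- Default missed, 2.0 used: 9.57 × (2 − 1) = +9.57 as printed; 9.57 × ln 2 = +6.63 log.

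Both show worsening; the second understates it. For the creatinine term to improve from Day 1 under the default, Day 1 creatinine must exceed 4. The highest creatinine compatible with CLcr 30 is (140 − age) × weight / (72 × 30):
- man of 55 years, 80 kg: 85 × 80 / 2160 = 3.15 mg/dL;
- man of 40 years, 100 kg: 100 × 100 / 2160 = 4.63 mg/dL.

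A Day 1 value above 4 is possible but needs a young or heavy subject, or a rise after Screening. With dialysis unrecorded, improvement needs a Day 1 value above the post-dialysis value.

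**Step 4. Effect on the mean.** The documents give no dialysis rate. Assume 0 to 3 of 50 subjects with unrecorded dialysis at a visit, each measured at 2.0:
- log: 3 × 6.63 / 50 = 0.40, so 0 to 0.4 points;
- printed: 3 × 19.14 / 50 = 1.148, so 0 to about 1.1 points.

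Three of 50 undialysed subjects at 6 mg/dL, scored without a cap, would shift the mean by 3 × 3.88 / 50 = 0.23 on the log form.

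**The case against.** A reader might infer that starting dialysis makes the MELD endpoint improve. The documents do not support that in general. The endpoint is change from Day 1, not from the last visit before dialysis, and the renal exclusion at Screening keeps most Day 1 values below 4. Step 3 shows that the ordinary result is still a worsening.

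A reader might also run the two gaps together. They act by different routes: the missing cap matters when dialysis is known, and the missing record matters when it is not, because the default is then never applied.

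Nor does the protocol hide dialysis altogether. Section 7.1.1 excludes procedures as AEs but requires the underlying condition to be reported where it is one. Section 7.1.3 makes laboratory abnormalities needing intervention reportable, and Section 7.3.2 collects SAEs throughout the study. The eCRF is not shown, so the absence of a dialysis item is established only for the protocol's schedule. These routes give a signal, but none requires the dates that the rule needs. AEs and concomitant medications are not scheduled at posttreatment Weeks 12 and 24, although chemistry is drawn then. Section 7.6.2.2 also exempts direct sequelae of a liver transplant performed within the AE window.

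Finally, Section 8.4.2 leaves efficacy details to the statistical analysis plan, which could add a cap. That is fair, but the protocol has itself fixed the formula, the floor and the dialysis value. Followed as written, the rule gives the reversed order. That 4 mg/dL is meant as the worst renal value is an inference; the text calls it only a default.

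**Conclusion.** The point holds as a minor one. Section 6.5.7.1 ranks subjects inconsistently above 4 mg/dL: a creatinine of 5 or 6 without dialysis scores 9.6 or 19.1 points above a dialysed subject as printed, or 2.1 or 3.9 on a log form. The direction is the same under both readings, so the point does not depend on which was intended. Separately, the scheduled data do not supply the condition that triggers the default, and missing it can understate a subject's score by 19.1 points (printed) or 6.6 (log) if 2.0 replaces 4.

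For change from Day 1 the usual effect is a mis-sized worsening in a few subjects, with improvement rare. The effect on the mean is small and rests on the assumed 0 to 3 of 50 subjects and the assumed post-dialysis value. The primary endpoint, SVR12, is untouched.

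**What to change.** Two changes are needed, because neither closes the other gap.

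1. Add to Section 6.5.7.1: *For the MELD calculation, serum creatinine above 4.0 mg/dL is set to 4.0 mg/dL for all subjects.* The drop on starting recorded dialysis from a value above 4 then becomes 0.
2. Add one yes/no eCRF item at every visit with chemistry: dialysis twice within the prior week, or continuous venovenous hemodiafiltration within 24 hours of the sample. List it in Appendix 2.

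The cost is one sentence and one more field for sites to complete, with no extra test. The cap has a price: it removes differences among undialysed values above 4 mg/dL. The measured creatinine remains available in the laboratory data.
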